\$20 for completing the baseline, \$5/week for diaries with 5/7 days completed (or TLFB interview completed) plus a \$30 bonus for completing all 5 weeks, \$50 for final survey, and \$50 for qualitative interview (potential total: \$175). **Fidelity.** The research team will review all call recordings, code for treatment fidelity and collaborate with QC supervisors to review standard call quality metrics. Feedback will be provided to coaches. **Feedback from QCs.** Feedback from QCs on challenges with the EEC and recommendations for improvement, which will be used to refine the EEC prior to Phase 2. **Measures.** (Table 2.) Baseline. Standard QL registration includes demographic and tobacco use questions. Prior to randomization, participants will complete additional measures on ENDS and cessation medication use, knowledge and beliefs (questions from the empirical literature or developed to assess key misconceptions targeted by EEC education), and brief assessments of psychosocial functioning (depression, stress, anxiety). Treatment Adherence/ Engagement. Call completion, call minutes, and NRT sent from the QL are standardly captured data. Daily diaries. Participants will complete brief diary assessments on their use of ENDS, cessation medications, and traditional tobacco products, as well as cravings and an open-ended question on quit challenges (1-5 minutes to complete; procedures will be refined to facilitate completion during Phase 1 Pilot). Diaries can be completed (1) online via emailed mobile-optimized survey links or (2) via paper measures that will be returned by mail weekly. RAs will provide orientation to diary completion, and will closely track online completion and mailed surveys to provide reminders. Nonresponders (<5/7 days completed) will be contacted by a RA to complete a brief TLFB interview by phone. Multimodal Outcome Survey. The outcome survey will include measures used at Baseline (see Table 2) plus: (1) Program Satisfaction and Acceptability: assessed via a 10 Likert-rated item questionnaire (e.g., Would you recommend this to a friend?) and, for the EEC group only, several open-ended questions (e.g., what would you change about this program?) developed based on the methodology outlined by Dumas and Redish; (2) Treatment Adherence: questions will assess use of EEC educational materials (EEC only) and use of print materials (both groups); (3) SDM: the 3-item Collaborate scale will assess coach effort in helping participants understand quitting options, eliciting participant preferences, and integrating preferences in QP decision making, and (4) adverse events during treatment and specifically during ENDS or cessation medication use. Surveys will be emailed with a link for online completion, followed by multiple attempts to complete by phone, and finally a truncated paper survey will be mailed. Qualitative Interviews. After program completion, trained interviewers will conduct an interview to assess: (1) ENDS, NRT, and nicotine beliefs (relative harm, safety, long-term use), (2) quit strategies used and how and why ENDS were used during the program, (3) reactions to SDM model for QP development, and confidence in and adherence to QP, (4) use of and reactions to EEC print materials, (5) reactions to coaching calls and education from QCs, (6) why/why not callers would recommend the program and recommendations for improvement, and (7) diary completion experiences. Findings will be used to augment other data to determine readiness for Phase 2, as well as to refine the treatment and measures. **Criteria for Proceeding to Phase 2.** 8/10 participants would recommend the EEC to other ENDS users. 7/10 report improved knowledge about ENDS and NRT. 7/10 articulate QPs that include adaptive, but not maladaptive strategies. Iterative changes will be made to the EEC; if benchmarks are not met, we will recruit for Phase 1 until the EEC is ready.

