
**2.4d Statistical Analysis.** Participant baseline characteristics and program engagement will be summarized using proportions (with 95% confidence intervals (CIs)) and means (with SEs). We will use regression (and non-parametric rank sum tests) to examine primary hypotheses that, at 3-months, EEC participants will (1) have completed as many or more calls, (2) have satisfaction rates at least as high and rate QP development experiences more positively, and (3) report more accurate beliefs about ENDS, smoking, and quit medications, compared to TAU. Secondary outcome analyses will examine rates of 7-day point prevalence smoking abstinence and of ENDS and cigarette dual use. The control and EEC groups will be compared using logistic regression for binary outcomes or ANCOVA for continuous outcomes, while controlling for relevant baseline data (caller characteristics, nicotine dependence, smoking history). Diary data will be reviewed to categorize frequency and characteristics of ENDS, cessation medication, and cigarette use. We will explore correlates of outcomes based on product use reported on diaries to examine potential mechanisms that lead to smoking cessation or continued dual use of cigarettes and ENDS. Finally, we will explore potential group differences or moderators of treatment engagement and outcomes (e.g., gender, age, race/ethnicity, reasons for ENDS use).

We will address missing values multiple ways: 1) analyzing existing data (responders), 2) assuming worst case (smoking) for missing, 3) using multiple imputation, and 4) conducting sensitivity analyses with different non-responder relapse probabilities to determine how extreme values would need to be to invalidate results. For all aims, preliminary analyses will include summary statistics, cross tabulations of outcomes and baseline variables by group, and correlations. Standard regression diagnostics will be performed.

**Sample Size/Power.** Assuming 30% loss-to-follow-up, we will have 3-month outcomes for 35 per group, which aligns with Pilot/Stage I study recommendations. While this feasibility study is not powered to identify significant differences at the 5% alpha level, examination of CIs can identify outcomes or moderators worth investigation in a larger trial and inform treatment refinement, while avoiding over interpretation of effects.

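### SAP 2.4d does not name the baseline belief score as a covariate for primary hypothesis 3, although beliefs are measured before randomization and again at 3 months

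*SAP*

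**What the plan says.** SAP 2.4d (Statistical Analysis) sets the method for the primary outcomes in one sentence: "We will use regression (and non-parametric rank sum tests) to examine primary hypotheses". No covariate appears in it. The third hypothesis is that EEC participants will "report more accurate beliefs about ENDS, smoking, and quit medications, compared to TAU".

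The next sentence turns to secondary outcomes: "Secondary outcome analyses will examine rates of 7-day point prevalence smoking abstinence and of ENDS and cigarette dual use". After it comes the model sentence: "The control and EEC groups will be compared using logistic regression for binary outcomes or ANCOVA for continuous outcomes". The adjustment clause at the end of that sentence reads "while controlling for relevant baseline data (caller characteristics, nicotine dependence, smoking history"). Neither the baseline belief score nor, in general, the baseline value of an outcome is named in 2.4d. The protocol has no analysis section that would supply it.

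The score will be available:

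- **Baseline** (SAP 2.3b, Measures): "Prior to randomization, participants will complete additional measures on ENDS and cessation medication use, knowledge and beliefs". The items are described as "questions from the empirical literature or developed to assess key misconceptions targeted by EEC education".
- **Follow-up** (same paragraph): "The outcome survey will include measures used at Baseline (see Table 2"). The row of the measures table for knowledge and beliefs is marked at Baseline and at the Outcome Survey.
- **Phase 2** (SAP 2.3c, Measures): the Phase 1 measures carry over with three exceptions. One of them allows measures to change after Phase 1; none removes the baseline belief measure. Baseline measures come before randomization in both SAP 2.3c and the Phase 2 sections of the protocol.

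**The concern.** When an outcome is also measured at baseline, its baseline value is usually the strongest single predictor available. The three covariate groups listed in 2.4d would not ordinarily be taken to cover what a caller believes about ENDS or nicotine replacement at entry. As written, a model without baseline beliefs, or a rank-sum test, could be presented as the planned analysis of a primary hypothesis, and the choice could be made after the data are seen.

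Two things are at stake. The first is precision. The SAP says the pilot is not powered at the 5% level and will read its results through confidence intervals to decide what to take into a larger trial, so interval width is what the pilot delivers. The second is chance imbalance in entry beliefs, which at this sample size can noticeably shift one trial's unadjusted estimate. Beliefs are a direct target of the education component, and SAP 2.1 reports misinformation among dual users at registration, so entry scores are unlikely to be uniform.

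**Working it through.** **Inputs from the documents.** 100 randomized 1:1 (SAP 2.3c, Design); 30% loss to follow-up (SAP, Sample Size/Power).

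**Inputs assumed.** The baseline-to-3-month correlation r is set at 0.3, 0.5 or 0.7. The listed covariates, treated as one composite, explain w² = 10% or 20% of the 3-month score and correlate c = 0.3 or 0.5 with the baseline score. The documents give none of these. Results are in SD units of one belief score.

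**Step 1. The plan's own figure.** 50 × (1 − 0.30) = 35 per group. This reproduces.

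**Step 2. Gain over the covariates already listed.** The partial correlation is (r − wc) / √[(1 − w²)(1 − c²)], and the further cut in standard error is 1 − √(1 − partial²).

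- Worked example, r = 0.5, w² = 0.1, c = 0.3: (0.5 − 0.095) / √(0.9 × 0.91) = 0.448, a cut of 10.6%.
- Worked example, r = 0.5, w² = 0.2, c = 0.5: (0.5 − 0.224) / √(0.8 × 0.75) = 0.357, a cut of 6.6%.

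| r | Further SE cut over the four w², c combinations |
|---|---|
| 0.3 | 0.5–2.6% |
| 0.5 | 6.6–10.6% |
| 0.7 | 21.1–25.6% |

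**Step 3. Gain over a model with no covariates.** SE = √(2/35) = 0.239. The unadjusted half-width is t(0.975, 68 df) × 0.239 = 1.995 × 0.239 = 0.477 SD. With the baseline score (and one degree of freedom for gender), it is t(0.975, 66 df) × 0.239 × √(1 − r²):

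| r | Half-width (SD) | Equivalent unadjusted n per group, 35/(1 − r²) |
|---|---|---|
| 0.3 | 0.455 | 38.5 |
| 0.5 | 0.413 | 46.7 |
| 0.7 | 0.341 | 68.6 |

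Simulation with 4,000 trials per cell gave 0.458, 0.415 and 0.341 SD, with 94.6–95.2% coverage. The interval that goes with the rank-sum test had a half-width of about 0.49 SD.

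**Step 4. If education weakens the correlation in the EEC arm.** With TAU/EEC correlations of 0.3/0.1, 0.5/0.2 and 0.7/0.3, the simulated half-widths are 0.468, 0.449 and 0.416 SD, against 0.474–0.476 unadjusted: cuts of about 1%, 6% and 13%.

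**Step 5. Chance imbalance.** The between-arm difference in mean baseline score has a standard deviation of √(2/35) = 0.239 SD. A difference of 0.25 SD or more in either direction has probability 2 × [1 − Φ(0.25/0.239)] = 0.30. It shifts the unadjusted estimate by r × 0.25 = 0.075, 0.125 or 0.175 SD.

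**Step 6. If items are analysed singly as binary.** Assume 50% accurate in each arm. In a logistic model the 95% half-width of the log odds ratio is about 0.95 without the baseline answer. With it, simulation gives about 1.0, 1.1 and 1.4 at a within-item correlation (phi) of 0.3, 0.5 and 0.7. The conditional odds ratio is a different and larger quantity, so this is not lost power, but the interval does not narrow. On the risk-difference scale the gain returns: 1.96 × √(2 × 0.25/35) = 0.234, times √(1 − phi²) = 0.223, 0.203 and 0.167.

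**Step 7. The downside.** At r = 0 the simulated half-width is 0.479 against 0.475 SD (gender balanced within arm) or 0.481 against 0.473 SD (gender random): about 1–2% wider.

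**The case against.** The best counter-reading is that the plan already covers this. It names ANCOVA for continuous outcomes, the bracketed list need not be exhaustive, and the baseline value of the same measure is an obvious piece of relevant baseline data. Both named secondary outcomes are rates, so the ANCOVA clause probably reaches the primary outcomes. If so, a regression with no covariates would not follow the plan, and the proper comparator is Step 2, not Step 3. That stands, and it is why the gain over the listed covariates leads here. At r = 0.3 it is close to nothing. What remains is that the text does not name the score, and the sentence that does govern the primary hypotheses names no covariates.

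Two limits also stand. Belief scoring is not given, hypothesis 3 includes beliefs about smoking while the measures table names only ENDS and FDA-approved aids, and measures may change after Phase 1. And late responders receive a shortened survey (protocol, Phase 2, Follow Up Surveys); its content is in an attachment, so 35 belief scores per group is not assured.

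A reader might go further than the documents allow in three ways:

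- **That the SAP excludes the adjustment, or that the comparison is biased.** It does neither. Randomization makes the unadjusted estimate unbiased on average.
- **That baseline adjustment narrows every interval.** On the plan's logistic scale it does not (Step 6).
- **That leaving gender unnamed is a comparable gap.** Gender is the stratification factor and a demographic in the measures table, so it fits under caller characteristics. If it explained 2% of the variance, the half-width would move only from 0.475 to 0.474 SD.

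**Conclusion.** The point holds as a gap in commitment, not as an error in the analysis. SAP 2.4d leaves the baseline belief score unnamed for a primary hypothesis on which it will be available before randomization. No test is invalid, and the 35 per group is correct.

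The likely size is a further standard-error reduction of 0.5–3%, 7–11% or 21–26% beyond the listed covariates at r = 0.3, 0.5 or 0.7, with less if education loosens the link between entry and follow-up beliefs in the EEC arm. Naming the score also protects against an imbalance of 0.25 SD or more, which has about a 30% chance. These figures rest on 35 analysed per group, one continuous score, and correlations and variance shares that are assumptions. The change is worth making because it costs almost nothing and fixes a primary analysis in advance.

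**What to change.** Revise SAP 2.4d as follows.

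- Make the main analysis of hypothesis 3 an ANCOVA of the 3-month belief score on treatment and baseline belief score, together with the covariates already listed. State that gender, as the stratification factor, is counted among caller characteristics.
- Report the adjusted difference with its 95% CI, and keep the rank-sum test as a sensitivity analysis.
- State that the adjusted-model sentence covers the primary outcomes.
- If belief items are analysed singly as binary, adjust for the baseline answer to the same item and report a standardised risk difference with its 95% CI, since the odds-ratio interval would not narrow.

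The cost is SAP wording only; the measures are already scheduled. The one statistical downside is an interval about 1–2% wider if the baseline score turns out to be unrelated to the 3-month score.
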